4.4. PATIENT'S GLOBAL IMPRESSION OF CHANGE (PGIC)

The patient's global impression of change after treatment will be measured using the Patient's Global Impression of Change (PGIC) questionnaire. This questionnaire measures a patient's perception of how treatment has affected their level of activity, symptoms, emotions, and overall quality of life. Each descriptor is ranked on an intensity scale of 1 = Very Much Improved; 2 = Much Improved; 3 = Minimally Improved; 4 = No Change; 5 = Minimally Worse; 6 = Much Worse 7 = Very Much Worse. This test will be self-administered during study visits on Day 365.

Upon completion of the questionnaire, the study coordinator will check the questionnaire for completeness. Any omissions or ambiguous answers will be clarified by the subject prior to leaving the clinic. The PGIC can be found in Appendix 3. Note, the subject will be required to initial and date the PGIC.

5. EVALUATION OF ADVERSE EVENTS

5.1. **DEFINITIONS**

An Adverse Event (AE) is the development of an untoward medical occurrence or the deterioration of a pre-existing medical condition following or during exposure to an investigational product, whether or not considered causally related to the product.

An untoward medical condition can be symptoms (e.g., nausea, chest pain), signs (e.g., tachycardia, enlarged liver) or clinically significant abnormal results of an investigation (e.g., laboratory findings, electrocardiogram).

Conditions or diseases that are chronic but stable should not be recorded as an AE. Changes in a chronic condition or disease that are consistent with natural disease progression are NOT considered AEs and also should not be recorded on AE worksheets. These medical conditions should be adequately documented on the appropriate page of the study worksheet (relevant medical history and/or physical examination). However, medical conditions present at enrollment that worsen in intensity or frequency in a manner inconsistent with the natural course of the disease during the treatment or post-treatment periods should be reported and recorded as AEs.

An adverse reaction means any adverse event caused by a drug. Adverse reactions are a subset of all suspected adverse reactions for which there is reason to conclude that the drug caused the event.

Suspected adverse reaction means any adverse event for which there is a reasonable possibility that the drug caused the adverse event. For the purposes of IND safety reporting, 'reasonable possibility' means there is evidence to suggest a causal relationship between the drug and the adverse event. A suspected adverse reaction implies a lesser degree of certainty about causality than adverse reaction, which means any adverse event caused by a drug.

A serious adverse event (SAE) is any untoward medical occurrence which:

- Results in death:
- Is life-threatening;
- Requires inpatient hospitalization (admission to hospital with a stay > 24 hours) or prolongation of hospitalization which is not specifically required by the protocol or is elective;
- Results in permanent impairment of a body function or permanent damage to a body structure; or
- Requires medical or surgical intervention to preclude permanent impairment of a body function or permanent damage to a body structure.

Additionally, important medical events that may not result in death, be lifethreatening or require hospitalization may be considered SAEs when they jeopardize the subject or require medical or surgical intervention to prevent one of the serious outcomes listed above. Examples of such medical events include: allergic bronchospasm requiring intensive treatment in an emergency room or at home, blood dyscrasias or convulsions that do not result in inpatient hospitalization or the development of drug dependency or drug abuse. Medical and scientific judgment must be exercised when classifying events as serious.

Life-threatening means that the subject is, in the view of the investigator, at immediate risk of death from the AE as it occurred. It does not include an AE which, had it occurred in a more serious form, might have caused death.

Persistent or significant disability/incapacity means that the event resulted in permanent or significant and substantial disruption of the subjects' ability to carry out normal life functions.

An unexpected AE is an AE, the nature or severity of which is not consistent with the applicable product information (e.g., Investigator Brochure for an unapproved product). Expected means that the event has been previously observed with the test article and is identified and/or described in the applicable product information. It does not mean that the event is expected with the underlying disease(s) or concomitant medications. It is expected that certain disease states will have reoccurring adverse events some of which may be considered expected over time.

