5.2. ASSESSMENT OF AES

All AEs, regardless of severity, occurring following study drug administration by a subject must be recorded on the AE worksheet. This will include the following information:

- Description of the AE
- Date of onset
- Duration
- Frequency
- Severity
- Seriousness (yes/no)
- Treatment
- Outcome
- Relationship to study medication, injection procedure and/or underlying disease

All AEs and SAEs must be followed until resolution, or the condition stabilizes. The Investigator is responsible to ensure that follow-up includes any supplemental investigations as may be indicated to elucidate as completely as possible the nature and/or causality of the AE or SAE. This may include additional laboratory tests or investigations, histopathological examinations, or consultation with other health care professionals. The Sponsor or its designee may request that the Investigator perform or arrange for the conduct of supplemental measurements and/or evaluations.

5.2.1. **AE CAUSALITY**

The study investigator will determine whether an AE is related or unrelated to study medication, the procedure (intramuscular injection) and / or the underlying disease using the following criteria:

Not related: An adverse event that is not related to the use of the test article or administration procedure.

Possibly related: An adverse event that might be due to the use of the test article or administration procedure. An alternative explanation, e.g., concomitant study

product(s), concomitant disease(s), is inconclusive. The relationship in time is reasonable; therefore, a causal relationship cannot be excluded.

Probably related: An adverse event that might be due to the use of the test article or administration procedure. The relationship in time is suggestive. An alternative explanation is less likely, e.g., concomitant drug(s), concomitant disease(s).

Definitely related: An AE that is due to the use of the test article or administration procedure. The event cannot be reasonably explained by an alternative explanation – e.g., concomitant drug(s), concomitant disease(s).

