Appendix 1. Schedule of Evaluations

Helixmith Co., Ltd. Page 32 of 45 Protocol VMDN-003b/C CONFIDENTIAL

SCHEDULE OF EVALUATIONS AND VISITS

Procedure	Day 270 Up to 14 D prior to Day 365	12M Day 365 ± 14 D
Informed Consent	✓	
Safety and Efficacy Parameters		
Vital Signs		✓
Concomitant Medications		✓
Daily Pain and Sleep Interference Diary		✓
PGIC		√
Adverse Events		✓

Helixmith Co., Ltd. Page 33 of 45 Protocol VMDN-003b/C CONFIDENTIAL

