9.1. Adverse Events

Adverse events will be coded using the MedDRA coding thesaurus (version 21.0). All AEs recorded in the clinical database starting after the last visit on the VMDN-003 study will be considered a treatment-emergent adverse event (TEAE). All AE summary tables will include the number and percentage of subjects with an AE within a category, system organ class (SOC), and preferred term.

An overall summary of the number and percentage of subjects with TEAEs will be provided by treatment group. Frequencies and percentages of the following will be included: subjects with any TEAE, subjects with any TEAE leading to discontinuation, subjects with any TEAE leading to death, and subjects with any serious treatment-emergent AE (SAE).

The incidence of TEAEs will be summarized with frequencies and percentages by the following:

- SOC and PT
- SOC and PT by maximum severity
- SOC and PT by relationship to study medication
- SOC and PT by relationship to injection procedure.
- SAEs by SOC and PT
- AEs of special interest by SOC and PT

There are 4 types of AEs of special interest (AESI):

- Ophthalmological events that could potentially suggest causality related to HGF and its angiogenic potential
- Acute cardiac events

- Foot ulcers
- AEs related to pregabalin or gabapentin and their occurrence rates with in conjunction with VM202

Adverse event data will be summarized by treatment group and by treatment group within baseline gabapentin and pregabalin use.

All adverse events will be presented in a listing.

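### Protocol 5.1 lets sites leave off worsening they judge to be natural progression, with no exception for the SAP's events of special interest, so the primary safety endpoint can under-count them

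*Protocol*

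**What the plan says.** Protocol 5.1 opens with a broad definition. An AE includes "the deterioration of a pre-existing medical condition following or during exposure to an investigational product, whether or not considered causally related to the product". Two paragraphs later it narrows this for AE worksheets: "Changes in a chronic condition or disease that are consistent with natural disease progression are NOT considered AEs and also should not be recorded". The same paragraph then brings some events back. Conditions present at enrolment that "worsen in intensity or frequency in a manner inconsistent with the natural course of the disease during the treatment or post-treatment periods" are to be reported as AEs.

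For the changes that are kept off the AE worksheet, the paragraph names another place: "These medical conditions should be adequately documented on the appropriate page of the study worksheet (relevant medical history and/or physical examination" pages).

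Protocol 5.2 lists what is recorded for each AE, including "Relationship to study medication, injection procedure and/or underlying disease".

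The primary endpoint (Protocol 5.6.1, SAP 2.2.1) is the difference between VM202 and placebo in the occurrence of AEs. SAP 9.1 names four types of special-interest event. The first is "Ophthalmological events that could potentially suggest causality related to HGF and its angiogenic potential"; the others are acute cardiac events, foot ulcers, and events related to pregabalin or gabapentin. The protocol does not mention special-interest events, and neither document says how the natural-progression rule applies to them.

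**The concern.** Protocol section 1 justifies the extension by the growth potential of HGF. If VM202 made existing eye disease or foot ulcers progress somewhat faster, each case could look like ordinary diabetic progression to the treating site. The comparison with placebo is what can separate a drug effect from natural history. Protocol 5.1 asks the investigator to make that separation one patient at a time, before an AE record exists.

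An event left off the worksheet cannot be recovered later. SAP 6.1.7 builds TEAEs only from AEs in the extension's clinical database, and the DSMB reviews reported AEs (Protocol 5.6.4). Both the final tables and the safety oversight therefore sit behind the same filter.

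**Working it through.** The documents give no sample size, event rate or margin for the safety endpoint, so there is no stated figure to reproduce. The check compares the texts and then illustrates the effect on assumed rates.

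**1. Collection rule against analysis rule.** The footnote to SAP Table 14.3.1.1.1, repeated in the later TEAE shells, counts as treatment-emergent any pre-existing condition that worsens after the last VMDN-003 visit. It has no natural-progression exception. Protocol 5.1 keeps part of that worsening off the AE worksheet. The table would describe a wider set of events than the sites are told to record.

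**2. Where excluded changes go.** The only visit collects the diary, vital signs, concomitant medications, PGIC and AEs (Protocol 3.2 and 3.4). In Protocol Appendix 1 the block headed "Safety and Efficacy Parameters" lists the same five items. Neither medical history nor physical examination is scheduled, and no SAP output reports extension data from such pages.

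**3. What is exposed.**
- Worsening of a chronic condition that departs from its natural course: recorded, under 5.1.
- Events meeting a seriousness criterion: the SAE definition in 5.1 has no progression exception, and 5.4.1 requires reporting regardless of relationship to study medication. The protocol does not say which rule prevails if a serious event is also judged natural progression.
- Non-serious worsening of existing eye disease or foot ulcers that looks natural: no assured route.
- A first foot ulcer: ambiguous. It can be read as a new untoward occurrence or as a change in the underlying disease.
- An acute cardiac event: more naturally a new occurrence, and often serious.
- Pregabalin or gabapentin events: not disease progression.

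**4. Effect on the arm comparison (assumed inputs).** Recorded rate = true rate × (1 − share left out). Assume true rates of 10% on placebo and 20% on VM202.

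| Left out, placebo | Left out, VM202 | Recorded, placebo | Recorded, VM202 | Difference (points) | Ratio |
|---|---|---|---|---|---|
| 0% | 0% | 10% | 20% | 10 | 2.0 |
| 25% | 25% | 7.5% | 15% | 7.5 | 2.0 |
| 50% | 50% | 5% | 10% | 5 | 2.0 |
| 75% | 75% | 2.5% | 5% | 2.5 | 2.0 |
| 25% | 50% | 7.5% | 10% | 2.5 | 1.33 |
| 50% | 25% | 5% | 15% | 10 | 3.0 |

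With lower assumed rates of 5% and 10%, equal shares of 25%, 50% and 75% reduce the 5-point difference to 3.75, 2.5 and 1.25 points, and the ratio again stays at 2.0. Equal filtering multiplies the difference by (1 − share) and cancels from the ratio. Unequal filtering changes the ratio in either direction.

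Shares could differ by arm even if sites did not know the treatment. If VM202 made worsening visibly abnormal, more of it would be recorded under the carve-back. If it added mainly slow, ordinary-looking worsening, less would be. SAP 3.6 gives blinding as not applicable, so the documents do not establish that the judgement is made blind.

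**The case against.** A general definition followed by a stated exclusion is a rule with an exception, not a contradiction in itself. That stands: the opening AE definition is in tension with the exemption but does not refute it. The underlying-disease field likewise does not prove that natural progression was meant to be recorded, because new events and abnormal worsening can also be disease-related. The firm conflict is with the SAP's TEAE footnote.

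The carve-back is real protection, since clearly accelerated worsening must be recorded. Serious events have a separate route, and the special-interest shells (Tables 14.3.3.1.1 and 14.3.3.1.2) are titled for serious events, the group least exposed. Concomitant medications are recorded with their indication (Protocol 4.1), so a drug-treated complication leaves some trace. The worksheets themselves are not available here, so a history page may exist even though none is scheduled. All of this narrows the problem. It does not cover non-serious, ordinary-looking worsening in the overall TEAE tables, or in the special-interest summary of SAP 9.1, whose text is not limited to serious events.

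A reader might go further and infer that the rule removes the special-interest events from the primary endpoint and biases it towards no harm. The documents do not support that. The exemption concerns changes in a chronic condition, and the SAP does not describe its special-interest events as diabetic complications. The loss depends on site judgement, and its direction is not fixed unless the shares left out are assumed equal.

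Continuity with VMDN-003 is a weak objection to a change. The AE rule of VMDN-003 is not in these documents, but the extension's TEAE tables count only events starting after the last VMDN-003 visit.

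**Conclusion.** The concern holds in a limited form. Protocol 5.1 allows non-serious worsening of existing eye disease or foot ulcers to go unrecorded when it looks natural in the individual patient, leaves the status of a first foot ulcer unclear, and makes no exception for the SAP's special-interest categories. It disagrees with the SAP's TEAE footnote and sends the excluded changes to pages with no scheduled assessment.

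The result is possible under-ascertainment in the primary endpoint that no analysis can repair. Equal filtering in both arms dilutes the absolute difference in proportion and leaves the risk ratio unchanged; unequal filtering could bias either way. The size cannot be estimated: the rates and shares above are assumptions, and the protocol plans only descriptive analysis. This should be fixed. It does not by itself invalidate the safety comparison.

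**What to change.** Reconcile Protocol 5.1 and 5.2 with SAP 9.1 and the TEAE footnotes:

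- State in Protocol 5.1 that the natural-progression exemption does not apply to ophthalmological events, foot ulcers or acute cardiac events, whether new or worsened since the last VMDN-003 visit.
- Record these as AEs, and put the investigator's view of cause in the existing field for relationship to underlying disease.
- Correct the reference to history and examination pages, which this study does not schedule.
- Align the SAP's TEAE footnote with the final wording, so that it describes what sites were told to record.

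Stable chronic conditions stay unrecorded. Deleting the exemption altogether is a wider trade-off and is not needed to close this gap.

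The cost is a one-paragraph amendment and a site memo, a few more AE records, and a somewhat higher reported AE rate in both arms. No new procedure is required. The change has to reach sites before the Day 365 visits to be fully effective, because events are lost at recording.

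### Protocol 5.1 defines persistent or significant disability/incapacity but does not list it as an SAE criterion, so some substantial, non-permanent losses of function are serious only at the investigator's discretion

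*Protocol*

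**What the plan says.** The SAE definition in Protocol 5.1 opens "A serious adverse event (SAE) is any untoward medical occurrence which" and continues with five bullets. The first two are death and threat to life. The other three are:

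- the third, on hospital stays: "Requires inpatient hospitalization (admission to hospital with a stay > 24 hours) or prolongation of hospitalization", with exceptions for protocol-required or elective stays;
- the fourth, on lasting harm: "Results in permanent impairment of a body function or permanent damage to a body structure; or"
- the fifth, which extends the fourth to harm that treatment averts: "Requires medical or surgical intervention to preclude permanent impairment of a body function or permanent damage to a body structure".

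A paragraph on important medical events follows. Events that do not meet the main outcomes "may be considered SAEs when they jeopardize the subject or require medical or surgical intervention to prevent one of the serious outcomes listed above". It closes with "Medical and scientific judgment must be exercised when classifying events as serious".

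Two definitions come next. The first explains life-threatening, which is one of the five bullets. The second is "Persistent or significant disability/incapacity means that the event resulted in permanent or significant and substantial disruption" of the subject's normal functioning, and it explains a term that is not among the bullets. The term appears nowhere else in the available protocol or SAP text.

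Seriousness is a yes/no field on the AE worksheet (Protocol 5.2). It is used in site reporting (5.4.1), in sponsor reporting to FDA (5.4.2) and in the SAE summaries of SAP 9.1. The SAP gives no seriousness criteria of its own.

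**The concern.** A definition placed directly after that of a listed criterion suggests that the matching bullet was dropped. The omission would be harmless if the remaining bullets covered the same ground, but the definition is wider than they are. Two sites could then class the same disabling event differently while both follow the protocol.

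What is at stake is classification and what depends on it: expedited reporting and the SAE counts that sit beside the primary safety endpoint. Loss of walking or of vision is a plausible kind of event here. SAP 9.1 names ophthalmological events and foot ulcers among its events of special interest.

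**Working it through.** No arithmetic applies, so the check sets the clauses side by side and follows one event through them.

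**Test event.** An adverse event causes significant and substantial loss of function that is not permanent. There is no immediate risk of death, no hospital stay over 24 hours and no intervention to avert permanent impairment.

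**Step 1: the five criteria in Protocol 5.1.**

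| Criterion | Met? | Why |
|---|---|---|
| Death | No | By construction |
| Life-threatening | No | No immediate risk of death |
| Hospitalization | No | No stay over 24 hours and none prolonged |
| Impairment or damage | No | The bullet requires permanence |
| Preventive intervention | No | No such intervention was needed |

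The event meets 0 of 5. It does meet the definition of disability/incapacity, because that definition joins permanent disruption and significant disruption with an *or*.

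**Step 2: the fallback.** The important-medical-event clause has two limbs. One is jeopardy to the subject. The other is intervention to prevent an outcome in the list above it. The second limb points back to a list without disability. The first could fit the event, but the clause says such events *may* be considered SAEs. Serious status is therefore allowed but not required.

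**Step 3: consequences if the investigator marks it non-serious.**

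| Route | Unexpected event | Expected event |
|---|---|---|
| AE worksheet (Protocol 5.2) | Recorded | Recorded |
| Site report within 3 working days (5.4.1: serious or unexpected) | Sent | Not sent |
| 15-day IND Safety Report (5.4.2: serious, unexpected reactions and suspected reactions) | Outside | Outside in any case |
| TEAE and maximum-severity tables (SAP 9.1) | Included | Included |
| SAE row of Table 14.3.1.1.1; Tables 14.3.2.1.1 and 14.3.2.1.2 | Missing | Missing |
| Special-interest Tables 14.3.3.1.1 and 14.3.3.1.2, as shelled | Missing | Missing |

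The 15-day row matters only for events judged at least possibly related. The table rows apply to events that start after the last VMDN-003 visit, which is how the SAP defines treatment emergence. The last row follows from the shells, which are titled as serious events and count SAEs. The text of SAP 9.1 plans the special-interest summary without that restriction, so this consequence would disappear if the shells were brought into line with the text.

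**The case against.** The strongest case against the point is that the gap is narrow and most safeguards remain.

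- **The clause is broader than it first looks.** Jeopardy to the subject is a limb of its own and does not depend on the list. The protocol also requires judgment to be exercised. An investigator who reads the disability definition beside the one for life-threatening may well treat it as a seriousness term. This stands as a limit: such events are not barred from serious status. It does not remove the point, because exercising judgment is not the same as having to reach a given answer.
- **The fifth bullet already covers some disabling events.** Acute loss of vision or motor function treated to avert permanence is serious without discretion. This stands, and the affected class excludes it.
- **Some loss of function is not an adverse event.** Protocol 5.1 excludes change consistent with natural disease progression. An extra SAE bullet would not affect those cases.
- **Unexpected events are reported anyway.** Protocol 5.4.1 gives them the same 3-working-day limit. This stands for site reporting. It does not carry over to 5.4.2, where the 15-day report needs an event to be both serious and unexpected.
- **The primary endpoint is occurrence of adverse events, not of SAEs.** All AEs are recorded, the DSMB reviews all reported AEs (5.6.4), and severe intensity is defined by limits on routine activity (5.2.2). This stands. The effect is confined to the SAE and special-interest displays.

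A reader might infer that disabling events could go unreported or vanish from the safety analysis, or that the sponsor chose to exclude them from SAEs. The documents support neither reading. The events remain in the general tables, and the stray definition looks more like a lost bullet than a decision.

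**Conclusion.** The point holds as an internal inconsistency with a limited but real effect. The list and the definition in Protocol 5.1 do not agree. For a defined class of events the protocol leaves serious status to discretion although its own disability definition is met. That class is significant, non-permanent loss of function with no stay over 24 hours and no intervention to avert permanent impairment.

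Its size cannot be given: the documents contain no event rates, and the Investigator Brochure, which decides what is expected, is not available. The consequences are those in the last table under the working, and they arise only when the investigator does not use the important-medical-event clause.

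The conclusion rests on the protocol text alone. The seriousness options on the SAE form and in the EDC are not shown, so it cannot be said whether sites are already offered a disability option. If they are, practice may be sound, but the protocol would still disagree with its own form.

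**What to change.** Reconcile the two parts of Protocol 5.1 by adding a bullet to the SAE list, *Results in persistent or significant disability/incapacity*, and keep the existing definition as its explanation. Check that the seriousness criteria on the SAE form and in the EDC match the amended list, and add the option only if it is missing.

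The cost is one bullet in a protocol amendment and possibly one EDC option. The downside is that slightly more events will be classed and reported as SAEs. No analysis method changes.
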